1.c. Potential Risks. We believe this research will present minimal risk to human subjects. We do not anticipate any psychosocial harm, economic harm, legal jeopardy, or other side effects for participants in the RCT. There is the small possibility that some RCT participants may find some of the survey topics embarrassing or worrisome. However, surveys of this type are routinely conducted, with no ill effects to participants. Because surveys will be completed online in participants' homes (or elsewhere if they prefer) with the option to not complete each survey, we feel that this is a minimal risk. The instructions for the study surveys will clearly indicate that participants do not have to answer any questions that they do not want to answer. All communications for vaccine reminders (Out-U and Out-I groups only) will be sent via text message/email. We do not anticipate that any of these communications will contain information that would cause any psychosocial harm, economic harm, legal jeopardy, or other side effects. All reasonable efforts will be made to ensure the emotional safety and well-being of each participant. However closely monitored, there may be risk associated with loss of confidentiality of information. Lastly, there could be unlikely circumstances when the study team may need to breach confidentiality (e.g., if for medical reasons, as required by law, etc.).

2. Adequacy of Protection Against Risks

2.a. Recruitment and Informed Consent Procedures. During the RCT, we will randomize about 2100 YSMM who will be recruited from social media sites, existing online panels (e.g., Amazon Mechanical Turk), and through professional contacts (e.g., co-investigators distributing approved social media advertisements). Eligibility criteria will include: a) cisgender male; b) ages 18-25; c)

sexual minority (reports ever having oral or anal sex with a male or being sexually attracted to males; or identifies as gay, bisexual, or queer); d) lives in the US; e) has not received any doses of HPV vaccine; and f) did not participate in the pilot study. We will require men to read English and able to provide informed consent (inferred by completing the screener survey and consent form). All men will provide informed consent to participate in the RCT. The project website will provide participants with detailed information about the study prior to consent. For the RCT, participants will also be asked to provide medical record release (MRR), allowing for confirmation of HPV vaccination status during the study. The MRR form will be accessed through the project website and be managed using Research Electronic Data Capture (REDCap). A completed MRR form will not be required for study continuation.

2.b. Protection Against Potential Risk(s). Every means will be taken to minimize the risk associated with participating in this project. The autonomy of participants will be protected by informing all participants of the purpose of the study and allowing them to opt out of participation without repercuSSION. Participants will be able to withdraw from the study at any time, and they will be able to refuse to answer any question. Participants will be provided with study contact information in case they have any questions or concerns or experience any negative outcomes.

Several precautions will be taken to avoid any breach of confidentiality. Participant ID numbers will be used instead of names of participants on study-related documents and in the study databases. The ID numbers and names will be linked to a master list that will be accessible only to the study team. The master list will be kept in a computerized tracking system that will be password protected behind a firewall. All electronic files and databases will be kept on a password protected computer accessible only to study team members behind a firewall. This includes de-identified datasets. All paper-based study forms will be stored in locked file cabinets that are only accessible to study team members. For participants in the Out-I group, communications for the interactive vaccine reminder process will not include any confidential information. All study team members will complete National Institutes of Health (NIH) and institutional requirements in training for responsible research and the ethical treatment of human subjects. Documentation of completion of training will be maintained on file. If for medical reasons or as required by law, the study team may have to breach confidentiality.

3. Potential Benefits of the Research to Human Subjects and Others

There may or may not be direct benefits to the participants of this study. Potential benefits to the participants will come in the form of improved HPV vaccination knowledge and behaviors. The information learned from this study may benefit sexual minority men in the future. The participants and society in general will benefit from this study to the extent that the results improve our understanding strategies to improve HPV vaccination among sexual minority men. The benefits far outweigh the risks of this study, since the possible risks are minimal and because the possible benefit is so great.

4. Importance of the Knowledge to be Gained

Sexual minority men have high rates of HPV infection and HPV-related disease, and therefore YSMM can benefit greatly from HPV vaccination. We recently developed and pilot tested *Outsmart HPV*, the first HPV vaccine intervention for YSMM that we are aware of. This study is the necessary next step in this line of research and will comprehensively evaluate the *Outsmart HPV* intervention. In doing so, it will provide an evidence base regarding the intervention's efficacy (including what type of HPV vaccine reminders are most effective for the intervention), mediators, and moderators. We will make every effort to present findings at scientific meetings and to publish findings in peer-reviewed journals.

5. Data and Safety Monitoring Plan

We have developed a Data and Safety Monitoring Plan for this study. The purpose of the data and safety monitoring plan is to ensure the safety of participants, the validity and integrity of data, and the

appropriate termination of studies for which significant benefits or risks have been uncovered or when it appears that the study cannot be concluded successfully. Risks associated with participation in research must be minimized to the extent practical and the method and degree of monitoring should be commensurate with risk. The essential elements of the Data and Safety Monitoring Plan include: a) monitoring the progress of the study and the safety of participants; b) plans for assuring compliance with requirements regarding the reporting of adverse events; c) plans for assuring that any action resulting in a temporary or permanent suspension of the study is reported to the appropriate agencies; and d) plans for assuring data accuracy and protocol compliance.

Prior to the initiation of the project, all study team members will receive standardized training to ensure that the activities of the study are conducted in a uniform, safe, confidential, and secure manner. The project website contains an administrative console that will allow the study team to document and monitor study activities (e.g., recruitment, data collection, etc.). Study team meetings will take place on a monthly basis to monitor study activities and to continually reassess the progress of the study, including assessments of data quality, timeliness, participant recruitment, accrual, retention, protocol compliance, and monitoring of the risk versus benefits throughout the study period.

All adverse events will be reported according to the policy outlined by the IRB at OSU. The appropriate forms will be completed and sent in accordance to the timeline set forth by the IRB. All adverse events will be reported to and reviewed by the study team. All protocol violations will be documented and reported to the IRB. Also, any privacy violations will be reported to the IRB and the institutional privacy offices. All privacy violations, adverse events, and protocol violations will be reviewed by the multi-PIs (Drs. [name] and [name]) and the rest of the study team. [name] will be responsible for reporting to the OSU Office of Responsible Research Practices/IRB and the NIH project officer. The IRB will be provided feedback more frequently if there should be any adverse events or other recommendations. [name] will also be responsible for reporting to the NIH project officer any action resulting in temporary or permanent suspension of the research project at OSU. These actions must be reported to the NIH project officer within 72 hours of notification. All documents or correspondence that are generated in the course of correcting or appealing the suspension status must also be forwarded to the project officer within 72 hours of it being presented to the institutional body that put forth directive to temporarily or permanently suspend the research project. During this time, no research project activities can occur.

[name] will be responsible for submitting reports, including annual reports to the OSU IRB and the NIH. Information included in the reports will include the number of individuals enrolled in the study, dropout rates, and any protocol deviations.

6. ClinicalTrials.gov and Good Clinical Practice (GCP) Training

This study will involve a randomized controlled trial of an HPV vaccine intervention for YSMM. Therefore, it will be registered in ClinicalTrials.gov. Throughout the ClinicalTrials.gov process, we will adhere to the policy recently released by the NIH. Specifically, we will: a) ensure registration to ClinicalTrials.gov occurs no later than 21 days after the first participant is enrolled into the randomized controlled trial; b) submit all required information during the registration process (descriptive, recruitment, location/contact, and administrative information); c) ensure results information is submitted no later than one year after the primary completion date of the randomized controlled trial; d) submit all required information during results reporting (participant flow information, demographics and baseline characteristics of enrolled participants, primary and secondary outcomes including results of any scientifically appropriate statistical tests, and adverse events); and e) update all submitted information once a year. Related, study team members will complete training in Good Clinical Practice (GCP) regarding clinical trials, as appropriate. This expectation was established by a recent policy statement from the NIH.

REFERENCES

6. National Cancer Institute. Surveillance, epidemiology and end results. <http://seer.cancer.gov/>. Updated 2014.

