In response to the low HPV vaccine coverage among YSMM, we received funding from NCI (R21CA194831) to develop and pilot test a culturally appropriate HPV vaccine intervention for YSMM (the *Outsmart HPV* intervention). The intervention is an mHealth intervention that consists of: 1) population-targeted, individually-tailored content about HPV and HPV vaccine that is delivered via a project website; and 2) vaccination reminders sent via text message/email. For the pilot test, we used Facebook advertisements to recruit 150 YSMM from the United States. Results of the pilot study showed that *Outsmart HPV* increased both HPV vaccine initiation (45% vs. 26%) and completion (11% vs. 3%) compared to a control group. Initiation is receipt of one or more doses of the HPV vaccine series, and completion is receipt of all three doses recommended for young adults.

For the next step in this line of research, we recently received additional NCI funding (R37CA226682; originally awarded as R01CA226682) to test the intervention in a large RCT. This protocol focuses on this large RCT.

METHODS

1. Intervention Overview.

1.a. Intervention Development and Pilot Testing. We developed the *Outsmart HPV* intervention for YSMM under a previous protocol that was approved by both CSRC (OSU-15100) and IRB (2015C0079). We then pilot tested this mHealth intervention in a separate protocol (CSRC: OSU-15234 and IRB: 2016C0004). More recently, we submitted a protocol to make updates to the intervention based on results of our pilot study (CSRC: OSU-15234 and IRB: 2016C0004). The study described in this application is an extension of these prior protocols, as it will formally test the newly updated mHealth intervention in a large randomized controlled trial. The methodologies and materials included for this protocol are patterned heavily after those used successfully in our pilot study.

1.b. Theoretical Framework

The *Outsmart HPV* intervention was developed with a framework (Figure 1) that includes aspects of the Protection Motivation Theory (PMT),²⁰ Information-Motivation-Behavioral Skills Model (IMB),²¹ and the Minority Stress Model (MSM).²² The PMT is the base of the framework since it can predict vaccination behaviors,²³ but it is important to include

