2.c. T1 Survey. After project account setup, participants will begin their initial project website session, which will include completing the T1 (baseline) survey, viewing study materials online (either *Outsmart HPV* or control), and completing the T2 survey. The T1 survey will be completed on the project website and assess demographics, health characteristics, and theoretical constructs (about 15 minutes in duration; see Appendix). All survey items will be based on those used in past research.^{19,29-35} For all survey items (for the T1-T4 surveys), a reminder will appear if a participant tries to skip an item. The reminder will say, "Please answer each question." If participants still want to skip a question after the reminder is shown, they will be allowed to. For a few items, as indicated in the appendices included with this application, participants will be required to answer the question.

2.d. Randomization. Participants will next be randomized at the individual-level to a study arm: a) standard information about HPV and HPV vaccine (control group); b) *Outsmart HPV* that includes unidirectional vaccine reminders (Out-U); or c) *Outsmart HPV* that includes interactive vaccine reminders (Out-I). A 1:1:1 allocation scheme will be used, with assignments determined by an algorithm on the project website. Recruitment will continue until 2100 YSMM are randomized (700 per study arm).

2.e. Control Group. The control group will receive standard information about HPV and HPV vaccine (see Appendix). This content will be modeled after the Vaccine Information Statement (VIS) for HPV vaccine³⁶ (created by the Centers for Disease Control and Prevention) and viewed by control group participants on the project website. The VIS provides basic information about HPV and HPV vaccine. We modeled the control group content after the VIS because providers are required to give patients a VIS before vaccination.³⁶ Thus, the VIS may be considered the "standard of care." A printable version of this content will be available to control group participants for viewing/printing following completion of the T2 survey. If they wish, control group participants will also have the ability to log back into the portal after the T2 survey to view this content again (see Appendix for Re-accessing Information).

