2.m. Sample Size/Data Analyses. We will randomize about 2100 men (700 per arm), expecting 70% retention over the 9-month follow-up (based on our pilot study). We are confident in reaching this sample size given the large number of YSMM on social media and that similar sample sizes have been recruited via social media.^{64,65} All analyses will use an intent-to-treat approach.

Aim 1 (Efficacy). We hypothesize HPV vaccine initiation and completion will be higher among participants in both the Out-U and Out-I groups compared to participants in the control group (Hypothesis 1a). Further, we hypothesize that HPV vaccine initiation and completion will be higher among participants in the Out-I group compared to participants in the Out-U group (Hypothesis 1b).

We will first examine descriptive statistics (i.e., proportions and 95% confidence intervals [CIs]). We will then use logistic regression to test our hypotheses, with separate models for HPV vaccine initiation and completion. Models will control for any potential confounders (i.e., variables that differ between study arms [$p < 0.10$] at baseline). For each outcome, we will perform all pairwise comparisons of study arms, using a Bonferroni corrected two-sided alpha of 0.017 to control the overall type I error rate. We will have at least 80% power for all comparisons,⁶⁶ assuming our

projections of initiation (control=20%; Out-U=35%; Out-I=45%) and completion (control=10%; Out-U=22%; Out-I=35%). Projections are based on pilot study results and past work on different types of reminders.^{67,68} Logistic regression models will produce odds ratios (ORs) and 95% CIs. Results will determine the efficacy of *Outsmart HPV* and identify which type of HPV vaccine reminder most effectively increases vaccination.

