Aim 3 (Moderation). We will examine demographic and health-related characteristics from the screener and T1 surveys as potential moderators. We hypothesize intervention effects will be stronger (i.e., moderation) among YSMM who are not married or in a relationship (due to higher perceived vulnerability to HPV and HPV-related disease), live in urban areas (due to greater access to care, including LGBT-friendly providers), report having a routine medical check-up in the last year (due to higher utilization of healthcare and self-efficacy to get HPV vaccine), or report having disclosed their sexual orientation to a healthcare provider (due to higher self-efficacy to talk with a healthcare provider about HPV vaccine) (Hypothesis 3). We expect moderators will be similar for both HPV vaccine initiation and completion (which will be examined as separate outcomes).

We will use logistic regression models that include an interaction term between each potential moderator and study arm to test this hypothesis and identify moderators. Logistic regression models will produce ORs and 95% CIs. We will consider an interaction present if an interaction term has $p<0.05$. Given our analytic sample size, we will have 80% power to detect interaction terms with ORs>2.30. Results will determine if intervention efficacy differs by demographic and health-related characteristics.

2.n. Potential Challenges. Recruitment: We have expertise recruiting YSMM via social media^{26,44,73-77} and will offer study incentives. **Retention:** We expect 70% retention based on our pilot study and will provide incentives and survey notifications to aid retention. **Missing data:** Missing survey data will be minimized by using prompts for skipped items. This resulted in less than 5% missing data in our pilot study. **Outcome ascertainment:** HPV vaccination status will be confirmed by medical records if MRR is provided, otherwise self-reported data will be used. **Generalizability:** To maximize

generalizability, participants will be recruited throughout the US. YSMM recruited via Facebook in our pilot study were demographically similar to YSMM from nationally representative samples.²⁶⁻²⁸ **Contamination:** We do not expect contamination since we will recruit throughout the US, the project website will require login, and participants will receive only the study materials for their randomized study arm.

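### Aim 1 covariates are picked by a p<0.10 baseline test between randomised arms, so chance sets the model and predictors of vaccination are mostly left out; the cost is modest power, mainly for Out-I vs Out-U initiation

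*Combined protocol and SAP*

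**What the plan says.** Section 2.m, Aim 1 (Efficacy), plans logistic regression, with separate models for initiation and completion, and all pairwise arm comparisons at two-sided alpha 0.017. On covariates it says: "Models will control for any potential confounders (i.e., variables that differ between study arms" with p<0.10 at baseline. It names no Aim 1 covariate. It does not list the variables to be screened, or say whether the test is across three arms or pairwise.

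Other sections that bear on this:

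- Sections 2.c and 2.d: the T1 survey comes first, then "Participants will next be randomized at the individual-level to a study arm". No stratification factor is named.
- Section 2.c: many T1 items can be left blank: "If participants still want to skip a question after the reminder is shown, they will be allowed to". There are exceptions: "For a few items, as indicated in the appendices included with this application, participants will be required to answer the question".
- Section 1.b, on the theory whose constructs T1 measures: "The PMT is the base of the framework since it can predict vaccination behaviors".
- Section 2.m, Aim 3: "We will examine demographic and health-related characteristics from the screener and T1 surveys as potential moderators". Recent check-up and disclosure to a provider appear here, as moderators only.
- Section 2.m, opening paragraph: "All analyses will use an intent-to-treat approach". It does not say how men without follow-up enter the analysis.
- Section 2.n, on prompts for skipped items: "This resulted in less than 5% missing data in our pilot study".

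**The concern.** Confounding at baseline is not a risk that individual randomisation leaves open. Among all randomised men, the screen tests a null hypothesis known to be true, so it selects chance imbalances. If it were run only on retained men, differences could also reflect differential dropout; section 2.m does not say which set is meant, although all randomised men is the natural reading.

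Adjustment helps when the covariates predict the outcome, and the screen does not look at that. Two things follow. Strong predictors of vaccination are usually omitted, so the power they could give is lost. And the covariate set, and with it the conditional odds ratio, is not known until baseline data are in. Two analysts following the text could fit different models.

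In logistic regression the loss is not a wider standard error. Adjusting for predictors raises both the log odds ratio and its standard error, and power rises because the first grows proportionally more.

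**Working it through.** **1. The plan's power figure.** Inputs from section 2.m: 700 per arm, 70% retention (700 × 0.70 = 490), alpha 0.017 two-sided (z = 2.387), initiation 20/35/45%, completion 10/22/35%. Pooled two-proportion power is Φ[(|p₁−p₂| − z·s₀)/s₁], where s₀ is the standard error under the null and s₁ under the alternative.

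Out-I vs Out-U initiation at 490 per arm: s₀ = √(2 × 0.40 × 0.60/490) = 0.0313 and s₁ = √[(0.35 × 0.65 + 0.45 × 0.55)/490] = 0.0311. So (0.10 − 2.387 × 0.0313)/0.0311 ≈ 0.81, and power is 79.2%. The plan states at least 80%, so its figure essentially reproduces.

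| Analysis set | Out-I vs Out-U initiation | Lowest of the other five |
|---|---|---|
| 490 retained per arm | 79.2% | 98.4% |
| All 700 per arm | 92.5% | 99.9% |
| 700 per arm, the 30% lost counted as unvaccinated (rates × 0.7) | 70.2% | 97.0% |

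Only this comparison has no power to spare.

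**2. How often the screen omits a predictor.** With one three-arm test each variable enters with probability 0.10, so it is omitted 90% of the time. If any of three pairwise p<0.10 counts, it is omitted about 77% of the time. With 20 candidates (assumed), about 2.0 or 4.6 variables enter on average. In the named-list simulations below, none of the four predictive variables was selected in 67% or 37% of trials.

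**3. Power under the rule and under a named list.** Three-arm trials were simulated (20,000 per case, 490 per arm, marginal initiation 20/35/45%, 20 screened variables), with a Wald test of Out-I vs Out-U at 0.017. The named list is two normal constructs correlated 0.5, two yes/no items, and age with no effect. The documents give neither the number nor the strength of predictors, so three strengths are assumed. Unadjusted power was 79.4–79.8%.

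| Case (OR per SD of each construct alone; OR of each yes/no item) | Rule, three-arm | Rule, pairwise | Named list | Gain, points |
|---|---|---|---|---|
| Weak (1.35; 1.25) | 79.4% | 79.4% | 80.5% | 1.1–1.2 |
| Middle (1.65; 1.5) | 80.3% | 80.7% | 83.2% | 2.5–2.9 |
| Strong (2; 2) | 80.5% | 81.7% | 86.2% | 4.5–5.7 |

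A smaller repeat of 3,000 trials per case gave gains of about 0.7, 3.0–3.4 and 5.1–6.4 points. An optimistic bound, three independent normal predictors at OR 2 per SD, gives 7.2–8.8. In the middle case with 700 analysed per arm, the rule gives 93.1/93.4% and the list 94.7%; with the lost counted as unvaccinated, 70.6/70.9% and 72.8%.

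**4. Odds ratio and standard error.** Unadjusted, the OR is (0.45/0.55)/(0.35/0.65) = 1.52 and the SE of the log OR is 0.131, a ratio of ln(1.52)/0.131 ≈ 3.20. With the named list the mean ORs are 1.54, 1.59 and 1.65 and the SEs 0.134, 0.138 and 0.144, ratios of about 3.22, 3.36 and 3.48. Under the rule the mean OR hardly moves (middle case 1.524 to 1.533 or 1.543). Within a single trial, its ratio to the unadjusted OR runs from 0.97 to 1.07 (three-arm) or 0.96 to 1.10 (pairwise), 5th to 95th percentile. The two readings of the screen disagree on significance in 2.3–3.9% of trials.

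**5. Type I error.** With 20/35/35% and the middle list: 1.85% unadjusted, 1.65% and 1.62% under the rule, 1.83% with the list (Monte Carlo SE 0.09, nominal 1.7%). Nothing is inflated.

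**6. Skipped items.** If 5% of men skip a covariate item, dropping them costs 2.0–2.3 points and puts the weak case at 78.3%, below the rule's 79.4%. Mean imputation stays within 0.1 point of complete data.

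**The case against.** The strongest reply is that little is at risk. The rule uses only baseline data and arm, never outcomes, so nobody can use it to pick a favourable result. Type I error holds, the average odds ratio barely shifts, and five of six comparisons have at least 97.0% power on any reading. If all 700 per arm are analysed, the sixth has 92.5%, and the middle-case gain is only 1.3–1.6 points. Adjusting for a list moves the odds ratio further from its unadjusted value than the rule does. All of this stands, and it limits the point to efficiency and a fixed model.

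The size of the gain does rest on assumed predictor strengths, and tenths of a point should not be relied on: two runs of one other scenario (three binary predictors at OR 1.5) differed by about 0.6 point. The spread from 70.2% to 92.5% comes from the undefined analysis set, which is a separate and larger matter that naming covariates does not settle. Check-up and disclosure are named in the plan as moderators, not as predictors of uptake, so the choice of covariates needs the study team's judgement.

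None of this favours the screen. It gains little over no adjustment, while a named list does better in every case examined provided that men with skipped items are kept.

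**Conclusion.** The concern holds. The p<0.10 screen lets chance choose the Aim 1 model, omits a given predictor of vaccination in about 77% to 90% of trials, and leaves the estimated odds ratio unfixed until baseline data are seen. It is a valid rule with no inflation of type I error. The cost is about 1 to 6 points of power on Out-I vs Out-U initiation (part of Hypothesis 1b), assuming 490 analysed per arm and the weak-to-strong range of predictors above. If predictors are weak the gain in power is negligible, and the case rests on fixing the model in advance. The change should be made because it is nearly free; the trial's validity does not depend on it. Confidence in the direction is high; confidence in the size is medium.

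**What to change.** In section 2.m, Aim 1:

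- Delete the p<0.10 screen.
- Name a short list of screener or T1 covariates expected to predict vaccination, for example baseline intention, self-efficacy, age, routine check-up in the last year and disclosure to a provider. Include them in every Aim 1 model whatever the observed balance.
- For any listed item that may be skipped, state that it is filled without reference to arm (overall mean or mode) or handled with a missing indicator, so that no participant is dropped.
- Report unadjusted odds ratios as supportive, and state that the adjusted odds ratio is conditional on the listed covariates.

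The cost is SAP wording and a little more analysis work. All the variables come from surveys already planned, with no added participants or procedures.
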